5.0 Participant Completion and Withdrawal / Discontinuation

5.1 Participant Completion

Participants will have completed the study once all protocol related activities have been completed.

5.2 Premature Withdrawal / Discontinuation

All patients have the right to withdraw at any point without prejudice to their treatment. If necessary, the Investigator may discontinue a patient at any time if it is considered medically necessary e.g. loss of mental capacity. The Investigator may also withdraw a patient if it is considered that the scientific, and therefore, ethical standards of the study are compromised. In addition, patients will be withdrawn from the study, at the Investigator's discretion, if they fail to wear the geko™ device as part of their standard care as directed by the treating physician. The reasons for withdrawal will be fully recorded in the patient's source documents and on the appropriate case report form.

If a participant is prematurely discontinued from the study at any time due to an adverse event (AE) or serious adverse event (SAE), the procedures stated in Section 9.0 must be followed.

6.0 Study Treatments

6.1 Method for Assigning Eligible Patients

The study aims to compare the skin adhesive strength of two hydrogel formulations (new vs current) to ensure that adhesion strength is at least equivalent if not superior

with the new formulation. As such, there is no objective to prove a causal relationship between a treatment and an outcome, therefore patients will be divided naturally into two sequential groups for comparison purposes only. This will also ensure that the T3 and XT-3 devices are not mixed during routine clinical use.

Group 1 patients will enter Phase 1 of the study. They will continue their treatment pathway with the geko™ T3 device as per hospital clinical protocol for VTE prevention. Group 1 patients will complete the 10-day study period, before Group 2 patients are consented and enter Phase 2 of the study. Group 2 patients will continue their treatment pathway as per hospital clinical protocol but with the geko™ XT-3 device.

As both the T3 and XT-3 devices are identical in terms of the treatment they deliver to patients, the treatment pathway for both group 1 & 2 patients will be unaffected. The devices differ only in the hydrogel used for adhesion to the skin.

6.2 Description of Device for Evaluation

The geko XT-3™ device is CE marked for use in humans (GB12/87339; SGS, United Kingdom Ltd). It is made from mylar (polyethylene terephthalate (PET)) and is enclosed in a polypropylene casing and has a hydrogel layer which will stick it to the skin. This hydrogel layer is composed of a new formulation hydrogel designated KM40C and has already been tested to current international biocompatibility standards in humans (ISO 10993). Please refer to Appendix 4 for fitting instructions.

6.3 Device Use

The geko™ T3 and XT-3 devices will be used.

6.4 Device Labelling

Devices will be labelled in accordance with all applicable regulatory requirements.

6.5 Device Storage, Handling, Application and Disposal

Patients will receive treatment with the device as part of their standard care for VTE prevention following acute stroke. Moreover, there is no requirement or need to provide specific labelling, storage, handling, application, and disposal instructions.

6.6 Device Accountability

Patients will be receiving treatment with the device as part of their standard care for VTE prevention following acute stroke, therefore there is no requirement to provide product accountability instructions.

7.0 Description of Protocol Procedures and Assessments

7.1 Assessment of Eligibility

The Investigator must assess a patient's suitability and eligibility for the study, especially with regards to the Inclusion and Exclusion criteria of this Protocol described in Sections 3.3.1 and 3.3.2.

Although potential participants will be in-patients hospitalised following acute stroke, in order to be eligible to participate all patients must be capable of giving consent for themselves. They must understand and be willing to participate in the study and be able to comply with all procedures and provide written informed consent. Patients who do not fulfil these requirements will not be recruited.

7.2 Informed Consent

In obtaining and documenting informed consent the Investigator must comply with applicable regulatory requirements, local SOPs and must adhere to Good Clinical Practice (GCP).

The investigator will explain to each participant the nature of the study, its purpose, the procedures involved, the expected duration, the potential risks and benefits and any discomfort it may entail. Each participant will be informed that the participation in the study is voluntary and that he/she may withdraw from the study at any time and that withdrawal of consent will not affect his/her subsequent medical assistance and treatment. The participant must be informed that his/her medical records may be examined by authorised individuals other than their treating physician. All participants for the study will be provided a participant information sheet and a consent form describing the study and providing enough information for participant to make an informed decision about their participation in the study. The participant must be given ample time to decide whether to participate in the study or not. The formal consent of a participant, using the approved consent form, must be obtained before the participant is submitted to any study procedure. The participant should read and consider the statement before signing and dating the informed consent form and should be given a copy of the signed document. The consent form must also be signed and dated by the investigator (or his designee) and it will be retained as part of the study records. The patient's medical record should clearly indicate that the patient is participating in this study.

7.3 Patient Profile / Demographics

For the purposes of this observational study, demographic information will be collected at baseline (Day 0) and include:

- Patient age in years
- Patient gender
- Date of stroke diagnosis
- Current mobility – is patient able to walk independently
- Adjunctive treatments to the geko™ device e.g. drugs, stockings

7.4 Application of geko™ Device and Collection of Device Performance Data

Patients will receive treatment with either the geko™ T3 or XT-3 device as part of their standard care for VTE prevention as per hospital clinical protocol. During daily review of the patient by a member of the healthcare team, the following information will be collected for a maximum of 10 days or until the patient is able to mobilize independently:

- Length of time device worn for since fitting (hours)
- Adhesion to patient's leg (score from very well to not at all)
- Use of additional fixation to keep the device in position.
- Patient comfort
- Patient sleep post-fitting
- Patient's current mobility
- Ease with which device fitted (score from very easy to impossible)
- Device setting
- Assess for any AEs

8.0 Statistical Analysis and Sample Size Determination

8.1 Statistical Analysis

The ability of the geko™ XT-3 device to adhere to skin will be numerically scored and compared to the geko™ T3 using a non-paired t-test for equivalence.

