2.1 Study Endpoints

2.1.1 Primary Efficacy Endpoints

- Skin adhesion performance of new hydrogel formulation KM40C during routine clinical use of the geko™ XT-3 device will be compared to that of the current formulation used in the geko™ T3 device. Skin adhesion will be observed and scored numerically for statistical comparison to test for equivalency of the two formulations (new vs current).

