8.2 Sample Size Determination

The sample size of 20 patients per phase has been determined using MIL-STD-105, a standard commonly used in the medical device industry to specify sample size and provide the basis for acceptance and rejection. We set an acceptable quality level (AQL) of 0.15 for the function of the new formulation hydrogel and using the C=0 sampling plan (Table 2), 100% testing of 80 devices with no failures would confirm that we meet our specified AQL.

If completed on 20 patients and assuming 4 days of use (on both legs), this equates to a minimum of 80 XT-3 devices to test the new formulation the same numbers would be required for the T3 device with current hydrogel formulation for statistical comparison.

Table 2: MIL-STD-105 Statistical Sampling Plan (C=0 Sampling Plan)

MIL-STD-1916																	
Verification Level	VII		VI		V		IV		III		II		I				
INDEX VALUE																	
AQL	.010	.015	.025	.040	.065	.10	.15	.25	.40	.65	1.0	1.5	2.5	4.0	6.5	10	
LOT SIZE		SAMPLE SIZE															
2 TO 5	*	*	*	*	*	*	*	*	*	*	*	*	5	3	2	2	
9 TO 15	*	*	*	*	*	*	*	*	*	*	13	8	5	3	2	2	
16 TO 25	*	*	*	*	*	*	*	*	*	20	13	8	5	3	3	2	
26 TO 50	*	*	*	*	*	*	*	*	32	20	13	8	5	5	5	3	
51 TO 90	*	*	*	*	*	*	80	50	32	20	13	8	7	6	5	4	
91 TO 150	*	*	*	*	*	125	80	50	32	20	13	12	11	7	6	5	
151 TO 280	*	*	*	*	200	125	80	50	32	20	20	15	13	10	7	6	
281 TO 500	*	*	*	315	200	125	80	50	48	47	29	21	16	11	9	7	
501 TO 1,200	*	800	500	315	200	125	80	75	73	47	34	27	19	15	11	8	
1,201 TO 3,200	1250	800	500	315	200	125	120	116	73	53	42	35	23	18	13	9	
3,201 TO 10,000	1250	800	500	315	200	192	189	116	86	68	50	38	29	22	15	9	
10,001 TO 35,000	1250	800	500	315	300	294	189	135	108	77	60	46	35	29	15	9	
35,001 TO 150,000	1250	800	500	400	4776	294	218	170	123	96	74	56	40	29	15	9	
150,001 TO 500,000	1250	800	750	715	476	345	270	200	156	119	90	64	40	29	15	9	
500,001 AND OVER	1250	1200	1112	715	536	435	303	244	189	143	102	64	40	29	15	9	

* Indicates entire Lot must be inspected 100%. **Note:** Acceptance number in all cases is zero.

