8.4 Analysis of Study Endpoints

8.4.1 Primary Efficacy Endpoints

The primary efficacy endpoint for the study is:

- the skin adhesion performance of new hydrogel formulation

KM40C used in the geko™ XT-3 device compared to that of the current formulation KMT10 used in the geko™ T3 device. As this is a cohort observation study, this will be a direct comparison between two different patient groups / cohorts (Groups 1 and 2) to evaluate efficacy.

Primary endpoint data from this observational study will be summarised descriptively. Continuous parameters may include mean, standard deviation, median, minimum, and maximum.

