 PATIENT NUMBER

0		
---	--	--

 PATIENT INITIALS

--	--

How easy was it to apply the geko™ device to the patients leg?

Very Easy 	Easy 	Difficult 	Very Difficult 	Impossible 
---------------------------------------	----------------------------------	---------------------------------------	--	--

If there were any difficulties, please provide a comment below:

How well did the geko™ device stick to the patients leg?

Very Well Remained attached 	Well Detached in small area 	Poorly Detached over large area 	Very Poorly Detached completely 	Not at all Would not stick at all 
--	--	--	--	--

If any level of detachment has been indicated, please provide a comment below:

Did the patient need any additional fixation to keep the geko™ device in position?

None 	Micropore Tape 	Adhesive Accessory 	OnPulse™ Knee Strap 
----------------------------------	--	--	---

If removed was the geko™ device easily re-applied?

Yes 	No 	N/A 
------------------------------	-----------------------------	------------------------------

Once applied, how comfortable for the patient was the geko™ device?

Very Comfortable 	Comfortable 	Uncomfortable 	Very Uncomfortable 	Extremely Uncomfortable 
--	---	---	--	---

If any discomfort has been indicated, please provide a comment below:

Which setting was the geko™ device set to?

1 	2 	3 	4 	5 	6 	7 	8 	9 	10 	11 

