-------------------------------	-------------------------------	-------------------------------	-------------------------------	-------------------------------	-------------------------------	-------------------------------	-------------------------------	-------------------------------	--------------------------------	--------------------------------

CASE REPORT FORM	BASELINE (DAY 0)			DATE (DD/MM/YYYY)				
STUDY SITE:	THE ROYAL STOKE UNIVERSITY HOSPITAL							
PRINCIPAL INVESTIGATOR:	[name]							
SITE NUMBER	0	2	5	PATIENT NUMBER	0		PATIENT INITIALS	

Has the patient experienced any Adverse Events since signing the Informed Consent?

Yes No

If yes, please comment below:

CRF completed by:

Print Name: _____ Signature: _____ Date: ____/____/_____

To be completed by Principal Investigator:

I am confident that the information supplied in this case record form is complete and accurate data.

Signature: _____ Date: ____/____/_____

Follow-up Day 1 (please note days 1-9 CRFs will be the same)

CASE REPORT FORM		FOLLOW-UP 1 (DAY 1)			DATE (DD/MM/YYYY)	
STUDY SITE: PRINCIPAL INVESTIGATOR:		THE ROYAL STOKE UNIVERSITY HOSPITAL [name]				
SITE NUMBER		0  2  5 	PATIENT NUMBER	0   	PATIENT INITIALS	

How many hours did the patient wear the geko™ device for?					_____ hours
How well did the geko™ device stick to the patient's leg?					
Very Well Remained attached 	Well Detached in small area 	Poorly Detached over large area 	Very Poorly Detached completely 	Not at all Would not stick at all 	

If any level of detachment has been indicated, please provide a comment below:

Did the patient need any additional fixation to keep the geko™ device in position?				
None 	Micropore Tape 	Adhesive Accessory 	OnPulse™ Knee Strap 	

If removed was the geko™ device easily re-applied?				
Yes 	No 	N/A 		

If no, please comment below:

Overall, how comfortable was the geko™ device for the patient to wear?				

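### The primary analysis compares mean scores on an uncoded five-level detachment scale, so fewer small lifts can offset more complete detachments and XT-3 can pass, or look better, while coming off completely more often

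*Combined protocol and SAP*

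**What the plan says.** Section 2.1.1 makes a numerically scored adhesion rating the primary endpoint. Section 8.1 states that it "will be numerically scored and compared to the geko™ T3 using a non-paired t-test for equivalence", which is a comparison of two means. No coding, equivalence margin or significance level is given.

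The score can come only from the Appendix 3 item "How well did the geko™ device stick to the patient's leg". It has five ordered answers: *Very Well* (remained attached), *Well* ("Detached in small area"), *Poorly* (large area), *Very Poorly* ("Detached completely") and *Not at all*. Each follow-up form carries this item once, although devices are fitted to both legs.

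For the primary endpoint, Section 8.4.1 adds a descriptive summary: "Continuous parameters may include mean, standard deviation, median, minimum, and maximum". Detachment frequency is not an endpoint in Section 2.1 or Section 8.4. Failures appear only in Section 8.2, where "100% testing of 80 devices with no failures" is the basis for the sample size. What counts as a failure is not defined there.

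**The concern.** The steps of the scale are not interchangeable. A device that lifts at one edge is still on the leg, and one that has detached completely is not. A mean treats them as exchangeable at a rate set by the codes. With equal spacing of one point per level, moving from *Well* to *Very Well* gains 1 and moving from *Very Well* to *Very Poorly* loses 3, so three fewer small lifts pay for one complete detachment. Because the codes are not fixed, the exchange rate is not fixed either.

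The aim in Section 2.0 is to show that XT-3 adheres at least as well as T3. If the new gel had fewer minor lifts but more outright fall-offs, the planned test could report equivalence, or a nominal advantage, and the planned summary would not show how many devices came off.

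**Working it through.** **Inputs from the protocol.** 20 patients per group (Section 3.2); five ordered levels (Appendix 3); unpaired t-test for equivalence (Section 8.1); 4 days of use assumed (Section 8.2).

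**Assumed, because the protocol is silent.** Codes 4-3-2-1-0; margins of 0.25, 0.5 and 1.0 points; two one-sided tests at 5% each; all category percentages.

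**Number of ratings.** Table 2 in Section 8.2 does give 80 for an AQL of 0.15 at lot sizes from 51 to 1,200. But 20 patients × 4 days × 2 legs = 160 devices. The figure of 80 matches one rating per patient-day: 20 × 4 = 80. The form collects one rating per day, so 80 worn-device ratings per group is the base used here.

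**Expected means.**
- T3, 80% *Very Well*, 20% *Well*: 0.80×4 + 0.20×3 = 3.80.
- XT-3, 95% *Very Well*, 5% *Very Poorly*: 0.95×4 + 0.05×1 = 3.85.

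XT-3 looks better by 0.05. Complete detachments expected in 80 ratings: 0.05×80 = 4 against 0.

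**Sensitivity to coding.** With codes 4-3.5-1-0-0, T3 is 0.80×4 + 0.20×3.5 = 3.90 and XT-3 is 0.95×4 + 0.05×0 = 3.80. The sign reverses on the same data.

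**One data set at exactly these frequencies (80 ratings each, treated as independent).**
- Variance for XT-3: 9×0.95×0.05×80/79 = 0.433. Variance for T3: 0.80×0.20×80/79 = 0.162.
- Standard error: √((0.433 + 0.162)/80) = 0.086.
- 90% interval: 0.05 ± 1.655×0.086, or −0.09 to 0.19. This lies inside ±0.25.

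**Simulated trials.** 20 patients per group, tests on patient means. Equivalence is declared when the 90% interval for the difference lies within ± the margin. Each range runs from clustered within patient (Dirichlet, concentration 3) to independent ratings.

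| Margin | 4 ratings per patient | 8 ratings per patient |
|---|---|---|
| 0.25 | 38–72% | 54–97% |
| 0.5 | about 98–100% | 99–100% |
| 1.0 | 100% | 100% |

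**A second example, in which T3 also has complete detachments.** In order of level, T3 = 48/28/2/2/0 and XT-3 = 60/10/2/8/0. Points lost from 4 are (28×1 + 2×2 + 2×3)/80 = 0.475 and (10×1 + 2×2 + 8×3)/80 = 0.475. The means are identical, with a 90% interval of −0.22 to 0.22 on independent ratings. Complete detachments are 8 (10%) against 2 (2.5%).

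**What the descriptive summary would show.** In the first illustration the median is 4 in both groups. The minimum shows that some device came off, not how many.

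**The case against.** The strongest reply is Section 8.2. It describes the sampling standard as a basis for acceptance and rejection, with an acceptance number of zero. If complete detachment were the failure and the rule were binding, a true 5% rate would give at least one failure in 80 independent ratings with probability 1 − 0.95^80 = 98%. This would largely close the gap. It does not stand as written, because failure is undefined, the rule is not carried into 8.1 or 8.4, and it makes no comparison with T3.

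Second, a tight margin gives some protection. This is partly right: at 0.25 the proportion of trials declaring equivalence falls to 38–97%. The protocol sets no margin, and a tight one lowers the risk without removing it.

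Third, the wording in 8.4.1 is permissive, so a table of categories is not barred. That is true, but it is not planned either.

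Some stronger readings are tempting and are not supported:
- A reader might infer that XT-3 could pass while detaching more often in every sense. In the first illustration, detachment of any degree is 5% with XT-3 and 20% with T3. Only complete detachment is worse.
- A reader might count 8 of 160 devices in that illustration. The form has one rating per patient-day, so 4 of 80 is the figure that matches the data.
- A reader might cite a case with 10% complete detachment against 10% small lifts (means 3.70 and 3.90). With 8 ratings it passes in 72–97% of trials at 0.5 but only 18–20% at 0.25. Nothing is offset there: XT-3's mean is simply worse, and passing reflects a wide margin.

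**Conclusion.** The concern holds for complete detachment. Following 8.1 and 8.4.1 as written, XT-3 can be declared equivalent, or show the better mean, while coming off completely more often than T3, and no planned output would show how often. The possibility follows from averaging this scale. Its size does not come from the protocol: the figures of 38–97%, 98–100% and 100% at margins of 0.25, 0.5 and 1.0 rest on assumed codes, percentages and clustering. They show that the outcome is plausible across a range of margins. They are not a forecast that KM40C will behave this way, nor do they show that a false declaration is near certain whatever margin is chosen.

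**What to change.** 1. In 8.4.1, report counts and percentages in all five categories by group.
2. In 8.1, define for each patient the proportion of worn-device ratings that are *Very Poorly* or *Not at all*, with *Poorly* or worse as a second cut. Keep the two cuts separate: pooled, 10% *Poorly* with T3 and 10% complete detachment with XT-3 would count as equal.
3. Estimate the XT-3 minus T3 difference with a confidence interval that treats the patient as the unit. Report it beside the mean-score test and weigh it in any statement that XT-3 is at least equivalent.
4. Fix the score coding and the detachment definition before any Phase 1 data are reviewed. Waiting until Phase 2 would allow them to be chosen with one group's results in view. Section 8.3 also disagrees with Sections 3.0 and 6.1 on which device Phase 1 uses.
5. State whether this detachment definition is the failure meant in 8.2, and whether the zero-failure rule binds.

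The comparison should not be a pass/fail gate. With equal true rates of 5%, 20 patients per group and a 5-point limit (one-sided 5%), a truly equivalent gel would pass only 36–65% of the time.

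The cost is SAP wording and one table from data already collected. The interval will be wide. At 5% in both groups with 80 independent ratings each, the 95% half-width is 1.96×√(2×0.05×0.95/80) = 6.8 percentage points. With an assumed within-patient correlation of 0.25 and 4 ratings each, it is 6.8×√(1 + 3×0.25) = about 9 points.

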4.2 Follow-up and Daily Application of geko™ therapy (Days 1-9)

During daily review of the patient by a member of the healthcare team, a new geko™ device will be fitted bilaterally as per standard care. In addition, the following information will be collected each day or until the patient is able to mobilize independently:

- Length of time device worn for since fitting (hours)
- Adhesion to patient's leg (rate from very well to not at all)
- Use of additional fixation to keep the device in position
- Ease of re-application if removed
- Patient comfort (rate from very comfortable to extremely uncomfortable)
- Patient sleep post-fitting
- Patient's current mobility

Fit new geko™ device bilaterally for VTE prevention as per hospital standard care. Devices fitted will be as per allotted patient group and study phase and the following post-application information recorded:

- Ease with which device fitted (rate from very easy to impossible)

- Adhesion to patient's leg (rate from very well to not at all)
- Use of any additional fixation to keep the device in position.
- Patient comfort (rate from very comfortable to extremely uncomfortable)
- Device setting (1-11)
- Assess for any AEs

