8.3 Treatment Groups

The following treatment groups will be assessed

Group	Description
Group 1 (Phase 1, n=20)	Standard care with hydrogel KM40C (geko™ XT-3)
Group 2 (Phase 2, n=20)	Standard care with hydrogel KMT10 (geko™ T3)

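### Section 8.1 names no unit of analysis for its unpaired equivalence t-test, although adhesion is rated daily in the same 20 patients per group; pooling the ratings as independent would make equivalence too easy to declare.

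*Combined protocol and SAP*

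**What the plan says.** Section 8.1 is a single sentence. Adhesion will be "numerically scored and compared to the geko™ T3 using a non-paired t-test for equivalence". It gives no unit of observation, per-patient summary, method for repeated ratings, alpha or margin.

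Other sections bear on the unit and do not agree:

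- Section 8.2 works in devices. For 20 patients, "assuming 4 days of use (on both legs), this equates to a minimum of 80 XT-3 devices", and "the same numbers would be required for the T3 device with current hydrogel formulation for statistical comparison".
- Section 8.3 works in patients. It lists each group with 20, for example "Group 1 (Phase 1, n=20").
- Section 8.4.1 calls the primary analysis "a direct comparison between two different patient groups / cohorts", and then says "Primary endpoint data from this observational study will be summarised descriptively". It does not mention the equivalence test.

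On data collection, section 4.2 says "the following information will be collected each day or until the patient is able to mobilize independently". Section 7.4 lists adhesion once per daily review, for at most 10 days. The case report forms in Appendix 3 carry one five-level adhesion item at Day 0, on each of Days 1-9 and at Day 10. They have no left/right field, although devices are fitted to both legs.

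**The concern.** An unpaired t-test assumes independent observations. Ratings from one patient share the same skin, leg shape and ward care, so they are likely to be positively correlated. Each patient wears only one formulation, so this correlation does not cancel in the comparison. It enlarges the true variance of the difference between groups, and a pooled test ignores it.

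In an equivalence test, a standard error that is too small gives an interval that is too narrow and therefore favours a finding of equivalence. The stated objective in section 2.0 is to show that the new hydrogel adheres at least as well as the current one, so the error would favour the new product.

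Patients also contribute unequal numbers of days, because they leave once they walk independently or if they withdraw. A pooled mean therefore gives more weight to those who stay longer. The direction of any resulting bias is unknown. Finally, the study is unblinded, and a unit not fixed in advance could be chosen after the results are seen.

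**Working it through.** **1. The plan's own figure.** In Table 2 of section 8.2, the AQL 0.15 column gives 80 for lot sizes from 51 to 1,200, so 80 is a correct table reading. It comes from a zero-failure sampling plan. There is no power or precision calculation for the t-test to reproduce. The device count does not follow from its stated inputs:

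- 20 patients × 4 days = 80
- 20 patients × 4 days × 2 legs = 160

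As the forms have one adhesion item per day, 20 × 4 = 80 is the number of daily end-of-wear ratings per group, not the number of devices.

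**2. Ratings per patient (m).** The forms give 1 (Day 0) + 9 (Days 1-9) + 1 (Day 10) = 11 ratings, of which 10 are end-of-wear. Four days of use give 4 end-of-wear ratings. I use m = 4 and m = 10. Section 4.2 also lists a post-fitting adhesion rating on Days 1-9 ("Devices fitted will be as per allotted patient group and study phase and the following post-application information recorded"), but section 7.4 lists adhesion once per daily review and the application block of the follow-up form has no such item. I do not rely on the larger counts.

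**3. Assumptions.** The documents give no intraclass correlation (ICC), alpha or margin. I assume ICC 0.1 to 0.7, two one-sided tests at 0.05 each, and margins in units of the SD of a single rating. The true difference is set exactly at the margin, which is the worst case.

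**4. Formulae.** Design effect DE = 1 + (m − 1) × ICC. The true standard error is √DE times the naive one. Pooled false-equivalence rate at the margin ≈ 1 − Φ(1.645/√DE). For example, with m = 4 and ICC 0.5, DE = 1 + 3 × 0.5 = 2.5, √DE = 1.58, and 1 − Φ(1.645/1.58) = 0.149. The 80 ratings are then worth 80/2.5 = 32 independent ones.

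| ICC | DE, m = 4 | True/naive SE | Worth of 80 ratings | Error | DE, m = 10 | True/naive SE | Worth of 200 ratings | Error |
|---|---|---|---|---|---|---|---|---|
| 0.1 | 1.3 | 1.14 | 62 | 0.075 | 1.9 | 1.38 | 105 | 0.116 |
| 0.3 | 1.9 | 1.38 | 42 | 0.116 | 3.7 | 1.92 | 54 | 0.196 |
| 0.5 | 2.5 | 1.58 | 32 | 0.149 | 5.5 | 2.35 | 36 | 0.242 |
| 0.7 | 3.1 | 1.76 | 26 | 0.175 | 7.3 | 2.70 | 27 | 0.271 |

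**5. Simulation.** Setting: 20 patients per group, Normal scores, equal days. At margins of 0.5 to 1.0 SD the pooled test agrees with the table: about 7-18% with 4 ratings and 12-28% with 10. A Welch test on patient means gives about 5% or lower throughout.

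**6. Small margins.** The formula fails when the margin is small relative to the standard error, because the test then rarely declares equivalence at all. With 4 ratings and a 0.3 SD margin, simulation gives a pooled rate of about 4-7%, against about 1% or less on patient means. At 0.25 SD the pooled rate is at most about 1%, which is below 5% but still above the patient-level rate. With 10 ratings and 0.3 SD, it remains 11-23%.

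**7. Ordinal scores and unequal days.** I repeated the check with five-level scores (assumed shares 60/25/9/5/1%), the ICC set on the scored scale, and days of use uniform from 1 to 7. The pooled error is about 8-20%, and patient means stay at about 5%. The 5 longest-staying of 20 patients then supply about 41% of ratings instead of 25%.

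**The case against.** The strongest reply is that no harm is shown, only an omission. It requires three conditions: that ratings are pooled, that they are positively correlated, and that an equivalence decision is taken. Sections 8.3 and 8.4.1 point to patients, the 80 in 8.2 belongs to a sampling plan, and 8.4.1 promises only descriptive summaries.

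Most of this stands. A reader might infer that the plan analyses 80 devices as independent observations. The documents do not say so, and the passages describing the groups lean the other way. But none of them reduces the ratings to one value per patient, and 8.2 asks for the same numbers in both groups for the statistical comparison. The descriptive wording in 8.4.1 does not remove the test either: section 2.1.1 says adhesion is scored so that equivalence can be tested.

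A reader might also infer that pooling always pushes the error above 5%. It does not: with 4 ratings and a margin of 0.25 SD the rate is below 5%. What holds generally is that the pooled test is more liberal than the patient-level one.

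On the device count, 160 does satisfy a minimum of 80. The sentence nevertheless equates the product with 80, which is wrong as written.

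**Conclusion.** The point holds as a gap in specification that should be fixed. Section 8.1 leaves the unit open, and the two available readings have different standard errors. If ratings are pooled and positively correlated, equivalence is declared more easily than the data justify.

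The size rests on assumed values. At margins of 0.5 SD or more the problem is modest at ICC 0.1 with 4 ratings (about 7% instead of 5%). It is large at ICC 0.5 or above: about 15-18% with 4 ratings and 24-28% with 10. It matters only if the 8.1 test is used for a decision, which 8.4.1 leaves unclear. The documents do not support the conclusion that a wrong analysis is planned. Separately, the 80 devices in 8.2 conflict with the section's own inputs, which give 160.

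**What to change.** - **8.1:** Name the patient as the unit. Run the unpaired (Welch) equivalence test on one pre-defined adhesion summary per patient, for example the mean daily end-of-wear score.
- **8.1:** State in advance how a patient with only a Day 0 rating enters the test, including one whose device would not adhere at all. Otherwise a summary based on end-of-wear ratings could drop the earliest adhesion failures.
- **8.1:** State the numeric scores for the five labels, the alpha and the margin. The test cannot be run without them under any unit. The margin should come from the adhesion difference that matters, not from what the sample can power.
- **8.2:** Say that the comparison rests on 20 patients per group rather than 80 independent devices, and correct or reconcile 80 with 160.
- **8.4.1:** Refer to this test alongside the descriptive summaries.
- **Optional:** Add a mixed model with a random patient effect as a sensitivity analysis, noting that it weights patients differently when days are unequal.

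The cost is a few sentences and no new data. Intervals will be about 1.1 to 1.8 times as wide as pooled ones with 4 ratings per patient, over ICC 0.1 to 0.7. Apparent power also falls. With no true difference, 4 ratings, ICC 0.5 and an assumed 0.5 SD margin, it is about 25% on patient means against 66% pooled; at a 1.0 SD margin, power on patient means is about 98%. The precision given up is precision the data do not have.
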